#### 6.2 By Visit

Patients will be identified by the study staff screening patient records in collaborating wards. After conversation with the treating physician, a preliminary evaluation will be made regarding possible inclusion. After the patient has been thoroughly informed about the study and inclusion is deemed possible, all points mentioned in the above table will be carried out (flow chart 5.1). Informed consent must have been given voluntarily by each subject before any study specific procedures are initiated. Signed consent forms will be kept in a locked drawer inside the investigator's office.

Blood will be drawn early the following morning PRIOR to administration of NR/placebo. In addition to parameters mentioned in 5.1, NAD+ metabolites will also be measured. NR/placebo will be given shortly after this.

Staff at collaborating wards may contact the study staff out of hours.

#### 6.2.1 Before Treatment Starts

The following will be carried out prior to starting treatment:

- To evaluating patient eligibility, patients must meet all inclusion criteria and none of the exclusion criteria. The patient must give his or her informed consent and sign the appropriate paperwork. Please see table 1 for additional information.
- Baseline values of parameters used as end-points will be assessed (see 9.4)

#### 6.2.2 During Treatment

Patients will be monitored and assessed routinely as long as they remain in hospital. Possible adverse reactions are likely to occur during this time, and only patients thought to remain in hospital for at least 7 days are included. This allows the study staff to keep a close eye on all included patients. See 5.1 for detailed description of visits during and after hospitalization.

#### 6.2.3 End of Treatment Visit

An end-of-treatment visit will be carried out during the last week of treatment. For logistical reasons, and because potential effects of NR are assumed to be established prior to 90 days, we will allow for a window of 90 days +/- 7 days. Please see 5.1 for details.

#### 6.2.4 Withdrawal Visit

Patients who withdraw from the study will be followed up as described in the flow chart above (5.1).

#### 6.2.5 After End of Treatment (Follow-up)

Please see table 1 flow chart "End of treatment visit", "End of study visit" and "Follow-up period". Survival information and information regarding re-admissions will be collected using hospital charts and the causes of death registry until all participants are deceased.

#### 6.2.6 Criteria for Patient Discontinuation

Patients may be discontinued from study treatment and assessments at any time. Specific reasons for discontinuing a patient for this study are:

- Voluntary discontinuation by the patient who is at any time free to discontinue his/her participation in the study, without prejudice to further treatment.
- Safety reason as judged by the Principal Investigator
- Incorrect enrolment i.e. the patient does not meet the required inclusion/exclusion criteria for the study
- Patient lost to follow-up
- A female patient becoming pregnant (treatment will be stopped, but follow up continues as described otherwise).
- Deterioration in the patient's condition which in the opinion of the Principal Investigator or treating physician warrants study medication discontinuation.
- Compliance issues.

#### 6.3 Procedures for Discontinuation

#### 6.3.1 Patient Discontinuation

Patients who withdraw or are withdrawn from the study, will stop further treatment. Patients who withdraw will be followed up at the time of discontinuation and at the end of the study (see also flow chart 5.1). The reason for discontinuation will be recorded and significant adverse events will be followed up. All patients randomized will be included in the study population.

Patients who withdraw or are withdrawn from the study after randomization cannot be replaced.

#### 6.3.2 Trial Discontinuation

The whole trial may be discontinued at the discretion of the PI or the sponsor in the event of any of the following:

- Occurrence of AEs unknown to date in respect of their nature, severity and duration
- Medical or ethical reasons affecting the continued performance of the trial
- Difficulties in the recruitment of patients
- The project leader will immediately inform Helsetilsynet in the case of serious unexpected adverse events that are likely to be caused by the research.
- The project leader or other personnel are obliged to inform Helsetilsynet about research practices that might pose a danger to the safety of participants. In the case of deaths that can have been caused by the research the police should be informed.

#### 6.4 Laboratory Tests

Routine blood samples will be taken at all study visits. During hospitalization these samples will be taken as part of normal hospital routines and usually in the morning. The tests to be taken are listed in table 1, but minor changes may be amended at a later point.

It is beneficial for data analysis to obtain blood tests from as early on during the current illness as possible. Collection of such samples will be done in a pragmatic way by contacting the relevant biobanks or laboratories that might store samples from the participant. This may also include asking the laboratory to pre-emptively freeze patient samples instead of destructing them at the standard time.

Biobanking for other analyses will be performed immediately before the first capsule is administered. If not mentioned otherwise samples will be bio banked according to the groups own SOP (Standard Operating Procedure.

 A separate venous or arterial sample will be collected immediately before the first capsule is administered to analyze NAD+ and metabolites. This sample will be drawn by either the ward staff or the study staff depending upon the location of the patient and presence of existing arterial/venous access. Sampling will mainly be venous at the 90 day follow up when most participants will no longer be in-patients. The study staff will always be present to facilitate swift handling of the sample. This sample should be taken not more than 6 hours prior to the first capsule and at the same time of day on day 7 and 90 if at all possible. NAD+ is unstable and the sample must therefore be transported swiftly to the lab for immediate handling.

- 2) Cytokines (serum/plasma)
- 3) EDTA full-blood rapidly frozen for:
  - a) DNA extraction for DNA methylation arrays
  - b) Sequencing
  - c) SNP arrays
  - d) ChIP-seg and other molecular procedures
- 4) EDTA plasma for biochemical analyses and other analyses
- 5) WBCs for RNA seq
- 6) \*Urine
- 7) \*Buccal swab
- 8) \*Saliva
- 9) Frozen WBC for ChIP-seq/ATAC seq

\*Denotes samples that will only be collected from selected patients which probably will be the second and second last randomization batch (of 5+3 or 10+3 patients) and a similar number of healthy controls (matched by age and sex).

#### 7 Assessments

### 7.1 Assessment of Efficacy / Pharmacokinetic / Pharmacodynamic / Response

See 5.4 – laboratory tests for NAD+ metabolites. As these may cause unblinding, these results will be kept away from study staff until unblinding.

#### 7.2 Safety and Tolerability Assessments

Safety will be monitored by the assessments described below as well as the collection of AEs at every visit. Significant findings that are present prior to the signing of informed consent must be included in the relevant medical history/ current medical condition page of the CRF. For details on AE collection and reporting, please see flow chart 5.1 and point 7 below.

#### 7.3 Other Assessments

We hypothesize that recovery time after acute illness with tissue injury and inflammation will be reduced in patients supplemented with the NAD+ precursor NR. Hence, it is natural to collect data with regards to the following:

- Measure NAD+ levels before (before the first capsule is administered) during and after acute illness in patients using NR and placebo. See also point 5.4. We will connect the clinical outcome measures to the effect by measuring NAD+ level in peripheral blood mononuclear cells using liquid chromatography-mass spectrometry and histone acetylation using our own world leading ChIP-seq method (25).
- To investigate epigenetic mechanisms of how NR shortens recovery time after acute illness.
- See "Primary Endpoints" and "Secondary Endpoints" under section on Protocol Synopsis and section 9 below.

#### 8. Safety monitoring and reporting

The investigator is responsible for the detection and documentation of events meeting the criteria and definition of an adverse event (AE) or serious adverse event (SAE). Each patient, ward nurses and the treating physicians will be instructed to contact the investigator immediately if they manifest any signs or symptoms they perceive as serious.

The methods for collection and reporting safety data are described below. Despite NR's good safety profile and few expected side effects, all possible adverse events will be included in our study.

We will however refrain from reporting any other AE/SAE besides SUSARS in the hospitals own reporting system, Akilles, as this is putting an unnecessary strain on the reporting system.

#### 8.1 Definitions

#### 8.1.1 Adverse Event (AE)

An AE is any untoward medical occurrence in a patient administered the study intervention and which does not necessarily have a causal relationship with this treatment.

An adverse event (AE) can therefore be any unfavourable and unintended sign (including an abnormal laboratory finding), symptom, or disease temporally associated with the use of a medicinal (investigational) product, whether or not related to the intervention. The term AE is used to include both serious and non-serious AEs.

#### 8.1.2 Serious Adverse Event (SAE)

If an abnormal laboratory value/vital sign are associated with clinical signs and symptoms, Serious Adverse Event (SAE) is defined as any untoward medical occurrence, that at any dose:

- 1. Results in death
- 2. Is immediately life-threatening
- 3. Requires in-patient hospitalization or prolongation of existing hospitalization
- 4. Results in persistent or significant disability or incapacity
- 5. Is an important medical event that may jeopardize the subject or may require medical intervention to prevent one of the outcomes listed above.

Medical and scientific judgment is to be exercised in deciding on the seriousness of a case. We will be using the CTCAE (Common Terminology Criteria for Adverse Events, US department of Health and Human Services, V5, 2017) for guidance. Important medical events may not be immediately lifethreatening or result in death or hospitalization, but may jeopardize the subject or may require intervention to prevent one of the listed outcomes in the definitions above. In such situations, or in doubtful cases, the case should be considered as serious.

Hospitalization for administrative reason (for observation or social reasons) is allowed at the investigator's discretion and will not qualify as a serious adverse event unless there is an associated adverse event warranting hospitalization. Also, pre-planned hospitalization admission (i.e., elective or scheduled surgery arranged prior to the start of treatment) for pre-existing condition is not considered to be a serious adverse event.

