#### 8.3 Disease Progression

Events which are definitely due to disease progression (worsening of symptoms related to known acute or chronic illness that is known to fluctuate/expected to fluctuate in similar scenarios) will be recorded as AE or SAE in the study's own reporting system, but not in Akilles.

Death due to progressive disease during the treatment phase is to be recorded as a SAE or SUSAR as appropriate.

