7.1 Adverse Events

Adverse events were registered at each point of contact with the patient. Additionally, some adverse events were recorded after a participant made contact or if the investigator otherwise was made aware of any adverse event. Both adverse events reported by the patient and those recorded in hospital records, are registered.

Adverse events were recorded according to an event reporting system (Common Terminology Criteria for Adverse Events (CTCAE version 5.0)). The investigator graded each AE accordingly using the levels mild, moderate severe, life threatening or leading to death. For tabulations, only treatment emerging adverse events (TEAEs) will be presented. TEAEs are defined as AEs with a start date on or after date of first randomised treatment. Any AEs prior to treatment will be listed but not tabulated.

The number (%) of subjects with any TEAEs, with 1, 2 or > 3 TEAEs, with treatment related TEAEs, with treatment emerging serious AEs (TESAE) and TEAEs leading to study drug withdrawal will be summarized by treatment group. The number of events and number (%) of subjects with adverse events by system organ class (SOC) and preferred term (PT) will be summarized by treatment group, overall, for severe AEs and for AEs leading to study discontinuation.

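### The SAE definition in Protocol 8.1.2 opens with a stray laboratory or vital-sign condition that conflicts with 8.1.3, 8.3 and the rest of 8.1.2

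*Protocol*

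**What the plan says.** Protocol 8.1.2 opens its definition with: "If an abnormal laboratory value/vital sign are associated with clinical signs and symptoms, Serious Adverse Event (SAE) is defined as any untoward medical occurrence". Five criteria follow. Two of them are "Results in death" and "Requires in-patient hospitalization or prolongation of existing hospitalization"; the others cover immediate threat to life, lasting disability and important medical events.

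The rest of 8.1.2 does not repeat the condition. It leaves seriousness to judgement, points to CTCAE for guidance and, on important medical events and unclear cases, says: "In such situations, or in doubtful cases, the case should be considered as serious". An administrative admission "will not qualify as a serious adverse event unless there is an associated adverse event warranting hospitalization", a test in which laboratory values and vital signs play no part.

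The neighbouring sections are unconditional:

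- 8.1.1: "An AE is any untoward medical occurrence in a patient administered the study intervention". A laboratory finding is only one example of a sign.
- 8.1.3 lists the same five criteria for SUSARs.
- 8.3: "Death due to progressive disease during the treatment phase is to be recorded as a SAE or SUSAR as appropriate".

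Section 8.5 has its own rule for laboratory values and vital signs. Unexpected ones are recorded as adverse events, and those belonging to a reportable symptom, sign or diagnosis are treated as supporting information.

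The definition is put to use in three places. The opening of section 8 makes the investigator responsible for detecting events that meet it. Section 8.7.1 sets the notice times to the safety committee. SAP 7.1 summarises by treatment group the subjects "with treatment emerging serious AEs (TESAE"), without defining serious for itself.

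**The concern.** A seriousness definition should depend on the outcome of the event. This one makes the outcome criteria depend first on an abnormality linked to signs and symptoms. An investigator who applied the sentence as written could leave a serious event with no such abnormality off the SAE list. The event would then miss the 4-day or 1-day notice and be left out of the TESAE row in the SAP.

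SUSARs ought to be a subset of SAEs. As worded, an event can satisfy 8.1.3 without satisfying 8.1.2.

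The wording also matters because section 8 was revised in June 2023 to make adverse-event reporting clearer, and the current text still carries the clause.

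**Working it through.** No arithmetic applies to the wording, and the plan states no figure to reproduce. The check sets the passages side by side.

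**1. Where the condition applies, and what else would capture the event**

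| Criterion | 8.1.2, first sentence | 8.1.3 | Other reporting in the SAP |
|---|---|---|---|
| Death | conditional | unconditional | all-cause mortality (sections 5, 6.3) |
| Immediate threat to life | conditional | unconditional | adverse-event tables (7.1) |
| Admission or prolonged stay | conditional | unconditional | all-cause re-admissions (5, 6.4); prolongation only through length of stay |
| Disability | conditional | unconditional | adverse-event tables (7.1) |
| Important medical event | conditional | unconditional | adverse-event tables (7.1) |

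All five criteria are conditional in 8.1.2 and none is in 8.1.3. Section 8.3 also removes the condition, but only for death from progressive disease during treatment.

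**2. The first sentence applied to three constructed cases**

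- Re-admission for pneumonia with fever and high CRP: the condition is met and the event is an SAE.
- Fall with fracture and re-admission, with laboratory values and vital signs stipulated as normal: outside the sentence as worded. 8.3 does not apply. 8.1.3 would apply only if the event were judged an unexpected reaction to the product.
- Unexplained death at home on day 50 with nothing measured: unclear. The sentence does not say that the abnormality must be measured or recorded, and a dead patient has no normal vital signs.

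In logical form the sentence says: if A, then SAE is defined as B. It does not say what holds without A. The definition is therefore incomplete; it does not declare those events non-serious.

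**3. Likely origin.** 8.5 already deals with abnormal values tied to symptoms. The clause reads like a fragment of that rule placed in the wrong section.

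**4. What an absent label would change.** Section 8.7.1 requires notice of an SAE within 4 days, or 1 day if probably or definitely related. Its routine update to the committee appears to be fortnightly (the spelling is unclear). On that reading, an event without the label could reach the committee up to 14 days later, instead of within 4 days or 1 day. It would still be on the shared sheet shown in 8.7.1. In SAP 7.1 it would stay in the general adverse-event tables but not in the TESAE row.

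**The case against.** The strongest reply is that nobody would apply the sentence alone. 8.1.2 itself calls for judgement and resolves doubt towards serious. 8.1.3 and 8.3 carry no condition, 8.5 lists death and threat to life among the event outcomes, and the reporting sheet has SAE fields for cause of death and autopsy. The safety committee reviews clinical outcome before each dose step (8.9), not only labelled SAEs. Deaths and all-cause re-admissions are reported whatever their label. SAP 7.1 takes events from patients and from hospital records.

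Most of this stands, and it limits the consequence. It does not remove the contradiction. The doubtful-cases sentence depends on individual judgement, and a fracture with re-admission is not a doubtful case. 8.3 covers one cause of death. 8.1.3 does not cover serious events judged unrelated, which are still SAEs.

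A reader might infer that any death, fracture or re-admission without an abnormal value is not an SAE under this protocol. The documents do not support that. It follows only from reading one sentence in isolation, and the condition is an abnormality associated with signs and symptoms, not the mere presence of an abnormal value.

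A reader might also infer that the TESAE count is too low by some percentage, mainly after discharge. With the planned median stay of 15 days, (90 − 15)/90 = 83% of treatment days fall after discharge. That says nothing about how many serious events lack an abnormality, and a re-admission would ordinarily generate hospital measurements. The documents give no SAE rates, so any percentage would only restate an assumption.

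**Conclusion.** The point holds as an internal contradiction in an operative safety definition. The opening clause of 8.1.2 restricts the five criteria in a way that 8.1.3, 8.3 and the later text of 8.1.2 do not, and the passages must be reconciled.

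The possible effect is confined to two things: the timing of notice to the safety committee, and the TESAE row in SAP 7.1. Either would be affected only if an investigator applied the clause literally. Nothing in the documents shows that this happened, so no undercount should be stated. No estimand, efficacy test, population, sample size, power or alpha changes. The correction is worth making before lock because it is cheap and the SAP takes its notion of serious from this section.

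**What to change.** Delete the conditional clause from Protocol 8.1.2 so that the definition begins with the SAE term and runs straight into the five criteria, as in 8.1.3 and consistently with 8.3. Leave the rule on laboratory values and vital signs in 8.5.

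SAP 7.1 describes adverse-event recording in the past tense, so rewording alone does not settle events already classified. Before database lock, and blinded to allocation, go through the AE/SAE sheet for the 58 patients against the five criteria, correct any event whose SAE label turned on the clause, and record the number changed, including zero. Protocol 9.2 names both a single spreadsheet and the eCRF as source for adverse events, so confirm first which list is complete.

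The cost is one sentence in a protocol amendment notified to the ethics committee, and one pass through the adverse-event records of 58 patients. No new data are needed.

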#### 8.1.3 Suspected Unexpected Serious Adverse Reaction (SUSAR)

Adverse Reaction: all untoward and unintended responses to an investigational medicinal product related to any dose administered.

Unexpected Adverse Reaction: an adverse reaction, the nature or severity of which is not consistent with the applicable product information.

Suspected Unexpected Serious Adverse Reaction: Unexpected Adverse Reaction that is serious, i.e.:

- 1. Results in death
- 2. Is immediately life-threatening
- 3. Requires in-patient hospitalization or prolongation of existing hospitalization
- 4. Results in persistent or significant disability or incapacity.
- 5. Is an important medical event that may jeopardize the subject or may require medical intervention to prevent one of the outcomes listed above.

#### **8.2 Expected Adverse Events**

Previous studies have showed that NR in general is well tolerated. In a 2019 study of healthy, obese individuals it was found that type, incidence and severity of AE were similar across the different intervention groups and the placebo group. (Conze, D., Brenner, C. & Kruger, C.L. Safety and Metabolism of Long-term Administration of NIAGEN (Nicotinamide Riboside Chloride) in a Randomized, Double-Blind, Placebo-controlled Clinical Trial of Healthy Overweight Adults. Sci Rep 9, 9772 (2019). https://doi.org/10.1038/s41598-019-46120-z)

There were no statistically significant differences in the NIAGEN and placebo-groups with respect to any clinical chemistry parameter either, and no serious AE or reports of flushing were registered. Importantly, all AEs were resolved by the end-of-study.

No other animal- or human studies published have demonstrated any serious side effects of NR. In a study (reference 17 in the protocol) from 2017 there were no significant differences in the incidence of AEs in the intervention group compared to the placebo group. In the intervention group, six adverse events (mild nausea, moderate fatigue, mild headache, moderate dyspepsia, moderate abdominal discomfort and moderate diarrhoea) were possibly related to NR. All participants reporting AEs recovered and there were no SAEs reported in this clinical study either.

#### 8.3 Disease Progression

Events which are definitely due to disease progression (worsening of symptoms related to known acute or chronic illness that is known to fluctuate/expected to fluctuate in similar scenarios) will be recorded as AE or SAE in the study's own reporting system, but not in Akilles.

Death due to progressive disease during the treatment phase is to be recorded as a SAE or SUSAR as appropriate.

